5.4. Blinding and procedures for unblinding the study

5.4.1. Methods for ensuring blinding

The AZD3293 and placebo tablets used in the study will be identical in appearance, smell, and taste. Equal numbers of tablets will be dispensed to patients in each of the 3 treatment groups.

Packaging, labeling, and preparation of study medication will be performed in a way that will ensure blinding throughout the study.

Patients and their study partners will be unaware of the patient's randomized treatment assignment. No staff of the sponsor, CC , the investigational centers, or any other personnel involved in the conduct of the study on behalf of the sponsor will have access to the randomization scheme during the conduct of the study, except the personnel analyzing the PK and PD samples, responsible for the IVRS system, or preparing/managing the blinded study treatment kits or the Independent Statistical Center preparing the reports for the IDMC. The randomization list will be kept in a secure location until the end of the study and until all regulatory obligations have been met.

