2.2. Secondary and exploratory objectives

Table 1. Objectives and Endpoints

Double-Blind Treatment Period		
Secondary Objectives	Endpoints	
Clinical efficacy objectives: • To evaluate the efficacy of AZD3293 on functional, clinical, and cognitive outcomes in patients with early AD dementia at the end of the Double-Blind Treatment period (Week 104).	 Functional Outcome Measures The Alzheimer's Disease Cooperative Study Activities of Daily Living Inventory instrumental items (ADCS-iADL) score Functional Activities Questionnaire (FAQ) score Cognitive/Functional Outcome Measures Integrated Alzheimer's Disease Rating Scale (iADRS) score Clinical Dementia Rating – Sum of Boxes (CDR-SB) score Clinical Outcome Measures CDR-Global Score Neuropsychiatric Inventory (NPI) score Cognitive Outcome Measures Mini-Mental State Examination (MMSE) 	
To evaluate the relationship between treatment effect of AZD3293 and time (at points other than the end of the Double-Blind Treatment period [Week 104], such as Week 26, Week 52 and Week 78). Specific time points will vary by instrument.	ADAS-Cog ₁₃ , ADCS-iADL, FAQ, CDR-SB, and iADRS	
To test the hypothesis that AZD3293 will slow the rate of cognitive and functional decline associated with AD, compared with placebo	ADAS-Cog ₁₃ , ADCS-iADL, and FAQ using a slope analysis from a repeated-measures model	
To evaluate the efficacy of AZD3293 to prolong time in the current disease state	CDR global score	
To evaluate the clinical worsening and need for symptomatic treatments	AD symptomatic treatments time of initiation	

Biomarker objectives:	
 To evaluate the effect of AZD3293 on cerebrospinal fluid (CSF) amyloid beta peptide (Aβ) pharmacodynamics (PD) markers 	• CSF $A\beta_{1-42}$ and $A\beta_{1-40}$ concentrations
To evaluate the effect of AZD3293 on CSF markers of neurodegeneration	 CSF total tau and phosphorylated tau concentrations
To evaluate the effect of AZD3293 on brain amyloid burden	Florbetapir amyloid scan
To evaluate the effect of AZD3293 on brain aggregated tau levels	¹⁸ F-AV-1451 Tau PET [separate addendum]
To evaluate the effect of AZD3293 on brain metabolism	 Fluorodeoxyglucose (FDG) positron emission tomography (PET) [separate addendum]
To evaluate the effect AZD3293 on brain atrophy	Brain volumes measured by magnetic resonance imaging (MRI)

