This study will be randomized, double blind, and placebo controlled. Randomization and blinding of the patient, the patient's study partner, the investigator, and the Sponsor to the patient's treatment assignment are intended to minimize the potential for bias in the analysis of AZD3293 treatment effects. The placebo comparator will provide a reference for the changes in cognition and biomarkers due to disease progression as well as inform the safety profile of AZD3293 in patients with early AD.

Dosing and study duration

The AZD3293 doses selected for this study (20 mg and 50 mg, administered once daily) represent the projected therapeutic dose range based on their levels of inhibition of BACE1 in the CNS as calculated from the multiple-ascending-dose study CSF A β data. It is anticipated that 20-mg and 50-mg AZD3293 doses should achieve clinically relevant CSF A β reductions,

and the projected mean exposures at those doses should be well within the range of exposures shown to be safe and well tolerated in the Phase 1 studies. The 20-mg dose provided >50% mean reduction in CSF A β 1-42 concentrations over the dosing interval, and the 50-mg dose provided approximately 75% reduction in CSF A β 1-42 concentrations over the dosing interval. Thus, these 2 doses are deemed sufficient to demonstrate the efficacy of AZD3293 in this study. The PK variability is expected to be sufficiently low to ensure that individual patient exposures at these doses will also not exceed the levels already demonstrated to be safe and well tolerated.

The 104-week study duration is deemed adequate to detect the effects of AZD3293 on cognition, function, and biomarkers relevant to AD in the selected patient population. The potential for debilitating disease progression in the placebo-treated patients will be mitigated by the fact that all study patients will be maintained on standard of care.

Primary endpoint

The primary endpoint in this study is the change from baseline to Week 104 in the ADAS-Cog₁₃. The ADAS-Cog is a widely accepted, validated clinical outcome measure. The scale reflects domains and abilities that are central to the characterization of an AD patient's deficits in a clinical setting and its items are linked to meaningful aspects of the lives of patients and caregivers. Furthermore, the scale has demonstrated its ability to detect treatment differences in the span of MCI and mild AD (Orgogozo et al. 2004; Salloway et al. 2004; Aronson et al. 2009).

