6.5.2. Determination of drug concentration

Plasma and CSF samples for determination of AZD3293 and AZ13569724 concentrations will be analyzed on behalf of the sponsor by Covance or its designate, using appropriate bioanalytical methods. Full details of the analytical methods used will be described in a separate bioanalytical report. Samples from patients who received placebo may not be assayed for AZD3293 and AZ13569724 concentrations.

Additional analyses may be conducted on the biological samples to further investigate the presence and/or identity of drug metabolites or to investigate any potential dosing issues. Any results from such analyses may be reported separately from the Clinical Study Report.

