6.6. Pharmacodynamics

Pharmacodynamic outcome variables in this study include changes from baseline to the end of treatment in CSF biomarkers (concentrations of $A\beta_{1-40}$, $A\beta_{1-42}$, total tau, phosphorylated tau concentrations, and other, exploratory biomarkers [eg, sAPP β]), imaging biomarkers (amyloid PET and volumetric MRI), and plasma biomarkers relevant to AD.

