6.6.1. Cerebrospinal fluid biomarkers

Participants in the CSF longitudinal biomarker sub-study will have post-baseline CSF samples collected at Week 52 and Week 97 (or at discontinuation of study treatment if it has been at least 24 weeks since previous collection) for analysis of concentrations of $A\beta_{1-40}$, $A\beta_{1-42}$, total tau, phosphorylated tau, and exploratory biomarkers (eg, sAPP β , sAPP α , 5-x amyloid) (see Study Plan in Table 2). If a post-baseline CSF sample cannot be obtained because of procedural complications, patient issues, or patient request, it will not be considered a protocol violation.

Lumbar punctures should be scheduled at approximately the same time of the day at all visits to avoid the known circadian variation of CSF amyloid levels (Lucey and Bateman 2014). It is recommended that CSF samples be collected by insertion of an atraumatic spinal needle between vertebrae L3 and L5 (Vanderstichele et al 2012). Before performing the lumbar puncture procedure, the physician must take into account the overall assessment of the patient and bleeding risk.

CSF $A\beta_{1-40}$ and $A\beta_{1-42}$ are biomarkers for BACE inhibition that enable direct measure of the central PD of AZD3293.

CSF tau and phosphorylated tau concentrations are elevated in patients with AD. Elevations in concentrations of tau, as well as specific phosphorylated tau species, are thought to be markers for progressive neurodegeneration in AD. Accordingly, reductions from baseline in concentrations of CSF tau in patients who receive AZD3293 compared with patients who receive placebo may be indicative of reduced neuronal loss in AZD3293-treated patients.

Other CSF metabolites and/or protein species, including processed forms of APP such as sAPP β , inflammatory biomarkers, other recognized or as-yet unrecognized biomarkers, and, if appropriate, proteomics assessments may be examined. Biochemical signatures may help to explain differences in efficacy, safety, or tolerability and/or PK/PD related to AZD3293 treatment.

Detailed sample collection and handling procedures are provided in the Laboratory Manual.

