12.2.3. Multiplicity adjustments

The proposed study design contains several elements that require multiplicity adjustments to strongly control the family-wise error rate (FWER):

- Comparison of 2 AZD3293 treatment groups with the placebo group
- Changing the randomization ratio to 2:1 if a dose is dropped at the first or second interim analysis
- Sample size re-estimation at the second interim analysis

The first element, comparisons of the 2 AZD3293 treatment groups with the placebo group, is addressed by the use of a multiplicity graph. A graphical multiplicity strategy will be used for testing key secondary hypotheses to protect against Type I error of falsely rejecting a null hypothesis. The use of a prespecified analysis plan that employs Bretz' graphical approach will provide strong control of the study-wise Type I error rate for the primary and key secondary hypotheses at level α =0.05 (Bretz et al. 2009, 2011). The specific multiplicity graph will be detailed in the SAP.

In addition, to strongly control the FWER, a confirmatory adaptive design should satisfy the conditional invariance principle (Brannath et al 2007): separate test statistics will be calculated from the 2 patient cohorts (those patients enrolled prior to the second interim analysis [IA2], and those enrolled after IA2) and combined in a prespecified way (using the weighted inverse normal p-value combination method) for the final test decisions. Hence, any design modification that preserves the distributional properties of the separate test statistics under a given null hypothesis of interest will not lead to an inflation of the FWER. The p-value combination test principle combines the 2 p-values using a prespecified combination function and by construction satisfies the invariance principle. Details on the implementation of the measures to strongly control the FWER will be provided in the statistical analysis plan

A separate family of biomarkers will be tested at α =0.05. The family will include the biochemical biomarkers (CSF A β 1-42, total tau, and phosphorylated tau), as well as imaging biomarkers (amyloid PET and volumetric MRI).

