12.2.5. Biomarkers

Changes from screening to Week 97 in CSF biomarkers (eg, $A\beta_{1-42}$, total tau, and phosphorylated tau) will be analyzed using an MMRM analysis that includes the fixed effects of treatment, visit (categorical covariate), treatment-by-visit interaction, disease status at baseline (MCI due to AD or mild AD), APOE4 status (carrier versus noncarrier), and predose biomarker value (continuous covariate). An unstructured variance-covariance matrix will be used. The primary analysis is based on the treatment difference at Week 97 using least-squares means. The null hypothesis is that the difference in means between the AZD3293 group and placebo equals zero.

The primary analyses of estimates of global cortical load from amyloid PET and volumetric brain measures from MRI will be analyzed using the same methodology as described above for the CSF biomarker data.

In addition, amyloid PET data, including inter-individual patterns of baseline cortical load and intra-individual patterns of regional amyloid deposition, as well as eventual patient-level or regional differences in the longitudinal change of amyloid, will be explored in relation to AZD3293 treatment. Multivariate regression analysis will be performed on the level of global cortical amyloid load, the level of regional measures of amyloid binding and, potentially, on the level of single volume elements (voxels) of amyloid binding (parametric) images. Other imaging (ie, volumetric MRI) and non-imaging (eg, CSF biomarker, cognitive, demographic) data may also be explored as covariates in the analysis model.

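### Section 5.4.1 gives staff who analyze PD samples access to the randomization scheme without a stated need, so CSF total tau and phosphorylated tau may be assayed with the arm known

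*Protocol*

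**What the plan says.** Section 5.4.1 sets a general ban on access to the randomization scheme during the conduct of the study. It then lists those exempt: "except the personnel analyzing the PK and PD samples, responsible for the IVRS system", those who prepare or manage the blinded kits, and the Independent Statistical Center. No purpose, limit or sample type is attached to the PK/PD exemption.

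Section 6.6 defines the PD variables: "Pharmacodynamic outcome variables in this study include changes from baseline to the end of treatment in CSF biomarkers", with A-beta 1-40, A-beta 1-42, total tau and phosphorylated tau named.

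Table 1 in Section 2.2 makes the tau markers secondary endpoints, under the objective "To evaluate the effect of AZD3293 on CSF markers of neurodegeneration". Section 12.2.3 sets up a separate biomarker family at alpha 0.05: "The family will include the biochemical biomarkers", namely CSF A-beta 1-42, total tau and phosphorylated tau, plus imaging measures. Section 12.2.5 tests each against placebo at Week 97: "The null hypothesis is that the difference in means between the AZD3293 group and placebo equals zero".

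For drug concentrations only, Section 6.5.2 says: "Samples from patients who received placebo may not be assayed for AZD3293 and AZ13569724 concentrations".

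**The concern.** A laboratory that measures drug levels has a practical use for the code, since it can skip placebo samples. A laboratory that measures tau does not, because every arm must be assayed for the comparison to exist. The exemption nevertheless treats the two alike.

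An assay result depends in part on judgment: whether a run is accepted, whether a sample is repeated, whether an outlying value is kept. If the people making those decisions know the arm, a difference between arms can arise from handling rather than from treatment. The protocol gives these markers interpretive weight. Section 6.6.1 says that reductions in CSF tau "in patients who receive AZD3293 compared with patients who receive placebo may be indicative of reduced neuronal loss". A marker offered as support for disease modification should not carry an avoidable route to bias.

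**Working it through.** No stated figure is in dispute, so the check sets the sections side by side and then counts the exposure.

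**1. Do the tau assays fall inside the exemption?** Section 6.6 lists total tau and phosphorylated tau as pharmacodynamic outcome variables. Section 11.4.1 derives both under the heading for pharmacodynamic variables. Section 7.2.1, headed for PK and/or PD samples, covers the CSF collected for biomarker analysis. The staff who assay tau are therefore staff analyzing PD samples.

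**2. Is there a need for the code?**
- PK: yes, by inference from Section 6.5.2.
- PD: none stated. Sections 6.6.1 and 12.2.5 compare AZD3293 with placebo, so placebo CSF must be assayed.
- The early PK lock (Section 12.2.8) concerns PK data only and gives no reason for PD access.

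**3. Does another section withdraw the permission?**
- Section 5.4.2 holds codes for the planned analyses until evaluability decisions are documented. It governs code breaks and planned analyses and does not cancel the 5.4.1 exemption.
- Section 12.2.2 aims to confine emerging unblinded data to the IDMC and the Independent Statistical Center. Analysts holding both the scheme and biomarker results would be outside both groups, so this conflicts with 5.4.1 and does not cure it.
- Section 6.4.10 requires blind adjudication of cardiovascular events. No equivalent sentence exists for CSF assays.

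**4. Why A-beta is left out.** Section 3.3 reports "The 20-mg dose provided >50% mean reduction in CSF" A-beta 1-42, and about 75% at 50 mg. Changes of that size would largely reveal active treatment without the list.

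**5. Extent of the exposure.** Inputs: at least 175 CSF sub-study patients with lumbar punctures at Visits 12 and 19 (Section 3.1.1); a 40% missed post-baseline rate (Section 12.3.2.1); 2202 patients planned (Section 12.3.1).
- Scheduled post-baseline samples: 175 × 2 = 350.
- Scheduled tau and phosphorylated tau results: 350 × 2 = 700. At Week 97, the tested time point: 175 × 2 = 350.
- Evaluable patients: 175 × (1 − 0.40) = 105, and 105 / 3 = 35 per arm, which reproduces the protocol's figure.
- Share of the trial: 175 / 2202 = 7.9%.
- Share of the CSF markers in the tested family: 2 of 3.

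**6. Sensitivity, on an assumed bias only.** The protocol gives no basis for a bias size. Suppose handling shifted one arm by b standard deviations, with no true effect. For a two-sided t-test at alpha 0.05 with n = 35 per arm, the statistic has noncentrality b × √(35/2) on 68 degrees of freedom.

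| Assumed b (SD) | Total tau units (SD 61) | Phosphorylated tau units (SD 18) | False-positive rate per comparison |
|---|---|---|---|
| 0 | 0 | 0 | 5.0% |
| 0.1 | 6.1 | 1.8 | 7.0% |
| 0.2 | 12.2 | 3.6 | 13.1% |
| 0.3 | 18.3 | 5.4 | 23.6% |

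The table shows how sensitive a comparison of this size is. It is not an estimate of what would happen here.

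**The case against.** **PD might mean A-beta only.** Table 1 attaches the PD label to A-beta and puts tau under neurodegeneration, and Section 6.6.1 ties central PD to A-beta. This shows loose use of the term, but it does not outweigh Sections 6.6, 11.4.1 and 7.2.1. The samples also come from the same lumbar puncture.

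**The risk depends on facts not shown.** This stands as a limit. The protocol permits access but does not say it is used. The timing of the post-baseline biomarker assays is not stated; if they are batched after the study, the exemption has little effect. Section 6.6.1 leaves handling to the Laboratory Manual, which may already require coded samples, and assay-level blinding can reasonably be left to such a manual. But the protocol states an express permission, and a manual requirement would then sit beside contrary protocol text.

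**Removing the list does not by itself secure a blind tau assay.** This also stands. A-beta and drug levels from the same visits can reveal active treatment to anyone who sees them. That is a reason to add a second safeguard, and it does not justify giving out the scheme.

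**The counts are not an effect.** Agreed. The 700 results include Week 52, which enters the Week 97 contrast only through the repeated-measures model. At Week 97, at most 105 × 2 = 210 results would be available under the assumed missed rate.

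**Conclusion.** The concern holds, as a minor point. Section 5.4.1 grants a permission with no stated need, and it covers two of the three CSF markers in a formally tested family, in a sub-study of about 8% of planned patients. The conclusion rests on reading PD as Section 6.6 defines it and on the absence of any protocol sentence requiring blind CSF assay. It does not show that the assays are, or are likely to be, run unblinded, and no size of bias is claimed. Confidence is medium because the Laboratory Manual and the assay timing are unknown. ADAS-Cog13, the clinical secondary endpoints and their multiplicity graph are not affected.

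**What to change.** In Section 5.4.1, limit the laboratory exemption to personnel performing the drug-concentration (PK) bioanalysis. Then add wording such as:

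> Post-baseline CSF biomarker samples are assayed under coded identifiers by personnel without access to treatment assignment; run acceptance and repeats are decided before unblinding. Total tau and phosphorylated tau runs are accepted without reference to the same patient's A-beta or drug-concentration results.

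The last sentence deals with indirect unblinding, which removing list access alone would leave open. If the Laboratory Manual already requires coded, arm-blind assay, only the 5.4.1 wording needs aligning with it.

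The cost is a protocol wording change and a matching line in the Laboratory Manual, with no extra samples or assays. If the same staff run PK and biomarker assays, code access must be separated. If the same staff read A-beta and tau, tau acceptance must rest on criteria fixed in advance.

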5.4.2. Methods for unblinding the study

Individual treatment codes, indicating the treatment randomization for each randomized patient, will be available to the investigator(s) or pharmacists from the IVRS/IWRS for use in emergency situations as described below. Routines for this situation will be described in detail in the IVRS/IWRS materials that will be provided to each center.

If a patient receives a treatment kit other than the one randomly assigned by the IVRS/IWRS, the site clinical research associate should be notified and the IVRS/IWRS should be notified and the site inventory updated.

The treatment code should not be broken except in medical emergencies when the appropriate management of the patient requires knowledge of the treatment randomization, unless otherwise specified in this Clinical Study Protocol. In the case of a medical emergency, the investigator should make all attempts to contact the sponsor-designated medical monitor or designee prior to unblinding. However, if this is not possible, it is still required to document and report the action to the sponsor.

The sponsor, or its pharmacovigilance agent, retains the right to have the treatment allocation code broken for SAEs that are unexpected and are suspected to be causally related to study medication and that potentially require expedited reporting to regulatory authorities. Treatment codes will not be broken for the planned analyses of data, unless otherwise specified for the interim analyses of this study (see Section 12.2.2) until all decisions on the evaluability of the data from each individual patient have been made and documented.

If the treatment allocation is unblinded, the patient will be discontinued from study participation. However, the patient should continue to be followed for safety follow-up as appropriate.

5.5. Treatments

5.5.1. Identity of study medication

AZD3293 (investigational product) will be provided as immediate-release tablets. Matching placebo will be provided (Table 3).

Table 3. Study Medication

Study medication	Dosage form and strength
AZD3293	Tablets (20 mg, 50 mg)
(investigational product)	
Placebo	Tablets to match AZD3293

Study medication will be dispensed at Visits 2 through 19 (see Study Plan in Table 2). Each kit box will have a unique kit number, and enough tablets will be dispensed for daily dosing until the patient returns for the next study visit. All study medication will be provided in blister packs and must be stored as per storage conditions in a secured area with limited access.

